5.2 SECONDARY ENDPOINTS

5.2.1 Event free survival

Event-free survival (EFS) [days] is the shortest duration of the following:-

- dates of assessment indicating 'progressive disease' on RESPONSE page of eCRF – date of randomisation + 1day,
- dates of assessment indicating 'clinical progressive disease' on DISEASS or RESPONSE-page of eCRF – date of randomisation + 1day,
- dates of assessment indicating 'progressive disease' on PAT_STATUS of eCRF – date of randomisation +1 day (for patients who have not been censored before, see below)
- death date – date of randomisation +1day.

Date of assessment refers here to the progt as given in the eCRF. If progt is missing then the corresponding examdt will be taken instead if available. Progression events are only taken into account if the corresponding date is before the start date of a new anti-leukemia therapy (see below for censored patients).

Patients not being assessed 'progressive disease', clinical progressive disease' or death during the trial will be censored as described below. These patients must be reviewed on a case by case basis by the trial statistician (TSTAT) and trial clinical monitor (TCM).

Right censoring rule for event-free survival (EFS):

Patients getting a new additional other anti-leukemia therapy recorded at the eCRF (follow-up) but not being assessed 'progressive disease', clinical progressive disease' or death before the new anti-leukemia therapy was started will be censored at the date of last disease assessment before the new anti-leukemia therapy was started (excluding follow-up).

Event-free survival censored [in days] is the time from randomisation to the date of last visit (Date of last visit (including follow-up) – date of randomisation + 1 day) for all other patients not being assessed 'progressive disease', clinical progressive disease' or death at the time of data base lock. Date of last visit does not include visit dates from follow-up where 'lost to follow-up' = yes.

EFS will be reported in days.

Patients without any response assessment (best overall response = no assessment) and without death will be censored with an EFS of 0. Otherwise the death date will be used.

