5.1.2 Event Free Survival

Event free survival (EFS) is defined for all patients that entered the trial, and measured from the date of randomisation to the date of disease progression (treatment failure), relapse or death from any cause, whichever occurs first (R06-0452).

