6.2.3.2 Follow-up visit

Follow-up visits will be performed after the EoT visit in case patients are not eligible for further treatment cycles until death, lost to follow-up or agreement between sponsor and coordinating investigator not to pursue further follow up visits. Follow-up visits should be performed at 12 weeks intervals or earlier if appropriate. Follow-up visits may also be performed by telephone interview in case the patient is unable to visit the investigator. The following will be obtained and / or performed.

- ! ECOG performance score

- ! AEs since last visit in case they occurred during the observational period (6 weeks after the last trial drug administration) or are considered drug-related (see [5.2.1](#) and [8.4.1](#))
- ! Follow-up of AEs in case they were not yet recovered at EoT
- ! Outcome: date death (if applicable), date of progression (in case, the patient experienced PD)
- ! Treatment with any other antileukaemia drug (report date of treatment and drug)

After approval of Protocol Revision I, Follow-up is completed 21 days after discontinuation of study drug.

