7.3.1.2 Assessment of the primary efficacy endpoint and derived variables

The primary endpoint for efficacy is best objective response derived from the data of all cycles. The primary analysis will be done for all patients of the full analysis set (phase II) for all treatment schedules separately. Each patient will be assigned to one of the response categories described in [section 5.1.1.1](#).

Each patient's best response will be used as a primary measure. To describe response over time, the proportions of patients in each response category will be tabulated at specified time intervals.

The number of patients with objective response (best response is CR or CRi) will be summarised. Patients will be followed up for assessment of response and progression until they progress, receive any other anti-leukaemia therapy, die, or until the trial ends. The observed length of follow-up and the number of patients available for analysis at each time point will determine the period of time covered in tables and figures.

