7.3.2 Secondary analyses

7.3.2.1 Assessment of the secondary endpoints and derived variables

Secondary endpoints related to efficacy will be event free survival, overall survival, relapse-free survival, and remission duration.

Event free survival, overall survival, relapse-free survival

Event free survival (EFS) is defined as the duration of time from randomisation to time of treatment failure (i.e. PD), relapse from CR, or death from any cause, whichever comes first. Overall survival is the time from randomisation until death. Relapse-free survival is defined only for patients who achieve CR and is measured from the date of attaining CR until the date of recurrence or death from any cause, whichever occurs first.

In case there is no occurrence of death or treatment failures until the last visit of the trial the time will be censored. The percentage of patients who are event free will be displayed at monthly or greater time intervals as appropriate.

The causes of death will be summarised, along with whether death was plausibly related to disease progression.

Remission duration, response rate at different time points

Exploratory analyses will be performed to determine the remission duration and the response rate after specified time intervals. Analysis of remission duration will only be done for patients who achieve CR.

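### SAP 5.2.1 contradicts itself on EFS deaths after a switch to new anti-leukaemia therapy, and its undeclared censoring rule departs from the protocol definition

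*SAP*

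**What the plan says.** **Protocol.** Section 5.1.2 measures EFS from randomisation to "the date of disease progression (treatment failure), relapse or death from any cause, whichever occurs first". Section 7.3.2.1 repeats the definition and gives the only EFS censoring rule: "In case there is no occurrence of death or treatment failures until the last visit of the trial the time will be censored". Neither section mentions new therapy. Section 7.3.1.2, on the response endpoint, follows patients for response and progression "until they progress, receive any other anti-leukaemia therapy, die, or until the trial ends". Section 6.2.3.2 says "Follow-up visits will be performed after the EoT visit in case patients are not eligible for further treatment cycles until death", loss to follow-up, or an agreement to stop. Those visits record "Outcome: date death (if applicable), date of progression (in case, the patient experienced PD" and any other anti-leukaemia drug.

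**SAP.** Section 5.2.1 takes EFS as the shortest of several durations. The death item has no condition attached. For progression, "Progression events are only taken into account if the corresponding date is before the start date of a new anti-leukemia therapy". The lead-in to the censoring rules sends to censoring only patients with neither progression nor death during the trial. The specific rule for patients who start new therapy is different: those without progression "or death before the new anti-leukemia therapy was started will be censored at the date of last disease assessment" before that therapy, with follow-up excluded. Section 4 lists four changes from the protocol, among them the relapse-free survival and remission duration definitions. EFS events and censoring are not among them. Section 7.5 plans Kaplan-Meier curves and an exploratory log-rank test, with no EFS analysis that ignores new therapy.

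**The concern.** Patients are often moved to another therapy because the current one is failing. If a patient switches before progression is recorded, censoring at the last earlier assessment removes that patient from the risk set shortly before a likely event. Such censoring is plausibly informative and would lengthen estimated EFS. The trial is open-label and response is assessed by the investigator without central review, so switching could differ between arms and distort the comparison.

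The wording also leaves room for two programmers to produce different EFS data sets. One could follow the event list and count a death after a switch; the other could follow the switch rule and censor it.

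**Working it through.** The documents state no EFS figure, so there is nothing to reproduce. The check has two parts.

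**1. The texts applied to one patient.** The patient switches therapy with no recorded progression and dies later.

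| Text | Result for EFS |
|---|---|
| Protocol 5.1.2 and 7.3.2.1 | Event at death, or at an earlier progression |
| SAP 5.2.1, event list | Event at death |
| SAP 5.2.1, lead-in to censoring | Not sent to censoring, because the patient died during the trial |
| SAP 5.2.1, rule for new therapy | Censored at the last assessment before the switch |
| SAP 5.2.2, overall survival | Event at death |
| SAP 5.2.3, relapse-free survival (if CR or CRi was reached) | Event at death; no censoring at new therapy |

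The specific rule conflicts with the protocol, with the rest of its own section, and with the SAP's handling of relapse-free survival.

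**2. Illustration of size.** From the documents: 43 patients per arm (protocol 7.6.2). Assumed, because the documents give no values: exponential EFS with true median 3.0 months in both arms, a share q switching without recorded progression, censoring one month before the true event, and a two-sided 5% log-rank test.

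- Event rate: λ = ln 2 / 3 = 0.2310 per month, so mean EFS is 1/λ = 4.328 months.
- Share with an event in the first month: 1 − exp(−0.2310) = 0.206. These patients cannot be censored a full month earlier, so two variants bracket the answer. Variant (a) lets them switch and censors them near day 0. Variant (b) lets only the other 0.794 switch.
- Events per 43 patients: (a) 43 × (1 − q); (b) 43 × (1 − 0.794q).

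| q | Events (a) | Events (b) | Kaplan-Meier median, months, (b) to (a) |
|---|---|---|---|
| 0% (protocol rule) | 43.0 | 43.0 | 3.0 |
| 10% | 38.7 | 39.6 | 3.2-3.3 |
| 20% | 34.4 | 36.2 | 3.4-3.6 |
| 30% | 30.1 | 32.8 | 3.6-4.0 |

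Log-rank rejection with no true effect (simulated):

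| Switching in the two arms | SAP switch rule | Protocol rule |
|---|---|---|
| Equal | about 5-6% | about 5% |
| 20% v 10% | about 6-7% | about 5% |
| 30% v 10% | about 10-13% | about 5% |

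The crude event-rate ratio (events per person-month) for 30% against 10% switching can be found directly. Person-time per patient is 4.328 − 0.794q in (b). In (a) it is 4.328 − 0.893q, where 0.893 = 0.206/0.2310.

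- (b): (0.762/4.090) / (0.921/4.249) = 0.186/0.217 = 0.86.
- (a): (0.700/4.060) / (0.900/4.239) = 0.172/0.212 = 0.81.

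The arm with more switching looks better although there is no true difference. A separate simulation placed the switch at 50-95% of the time to the event and censored at the last monthly assessment. It gave medians of 3.2, 3.5 and 3.9 months and a rate ratio of about 0.84, within these ranges.

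**The case against.** - **Progression.** Protocol 7.3.1.2 already ends follow-up for progression at other anti-leukaemia therapy, and the quoted SAP sentence applies the same limit. This stands in part. The sentence sits in the response section and is not an EFS censoring rule, and protocol 6.2.3.2 and 7.4 plan to collect later progression. The progression cut-off is therefore arguable. The protocol text does not extend to deaths.
- **Deaths.** A reader might infer that the SAP plainly drops every death after a switch. The documents do not support that: the event list and the lead-in both keep death. What stands is a contradiction in which the most specific rule censors. The planned case-by-case review does not resolve it, because as worded it covers patients with neither progression nor death during the trial.
- **Availability of events.** A reader might also infer that all later events will be on file. Follow-up is every 12 weeks, may be by telephone, and can be ended by agreement. Death dates should mostly be obtainable; progression after a switch is reported rather than systematically assessed.
- **Reach.** Anyone with progression recorded before the switch already has an event. Progression is defined broadly (it includes clinical deterioration), and end of treatment records its date. Many failing patients will therefore be counted; the documents do not say how many will not.
- **Importance.** EFS is secondary, its test is exploratory, and no decision rule uses it. The phase IIa comparison rests on response, and overall survival counts these deaths. This limits the weight of the point but does not remove the inconsistency.

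**Conclusion.** The point holds in limited form. The new-therapy rule in SAP 5.2.1 departs from protocol 5.1.2 and 7.3.2.1, is not declared in SAP section 4, and conflicts with the SAP's own unconditional listing of death. The clear departure concerns deaths after a switch in patients without earlier recorded progression.

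The size is illustrative throughout. On the stated assumptions, median EFS is inflated by about 0.2 to 1.0 month across 10-30% switching. False rejection rises noticeably only when switching differs strongly between arms. Equal switching leaves the comparison close to its nominal level, although both medians are still too long. It would go too far to say that the rule is shown to bias this trial, or to favour a particular arm: informative censoring is a reasoned risk here, and neither switch rates nor their direction are given. SAP 6.4 and section 9 were not in the available text and could not be checked.

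**What to change.** Reconcile SAP 5.2.1 so that the main EFS analysis follows protocol 5.1.2. Death from any cause should count whether or not new therapy has started, and so should progression or relapse reported in follow-up. Keep censoring at new therapy as a sensitivity analysis, state in that rule how later deaths are handled, and declare it in SAP section 4. Report by arm how many patients start new therapy without earlier progression, so that readers can judge the effect.

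The cost is SAP wording and one extra analysis run; no new data collection is needed. The drawback is that progression dates after a switch come from 12-weekly, possibly telephone, follow-up and are less precise. Death dates are much less affected.

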5.2.2 Overall survival

Overall survival [in days] = (date of death - date of randomisation + 1 day), for patients with known date of death.

Overall survival (Censored) [in days] = (date of last trial visit (or follow-up) - date of randomisation + 1 day), for patients who are still alive at time of data base lock. Date of last visit does not include visit dates from follow-up where 'lost to follow-up' = yes.

Overall survival will be reported in days.

5.2.3 Relapse-free survival, remission duration and time to remission

Relapse-free survival / Remission duration is defined only for patients with a best overall response of CR or CRi.

Relapse-free survival [in days] = (date of first recurrence of disease or death after entering the trial – date of first occurrence of CR or CRi after entering the trial + 1 day) for patients with a recurrence (this value should be positive).

Relapse-free survival (censored) [in days] = (date of last trial visit (or follow-up) - date of first occurrence of CR or CRi after entering the trial + 1 day) for patients who did not yet experience recurrence of disease or death at the time of analysis.

Remission duration is defined analogously with the exception of censoring patients that die before recurrence.

Time to remission [in days] = (date of first occurrence of CR or CRi after entering the trial – date of randomisation + 1 day) for patients with an objective response (this value should be positive).

Date of first recurrence of disease is given by the first date of being assessed as either 'progressive disease', 'clinical progressive disease' or death after the first occurrence of CR or CRi after entering the trial. If a patient has either no date of being assessed as either 'progressive disease', 'clinical progressive disease' or death or no occurrence of CR or CRi after entering the trial this date is missing and will also not be imputed.

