7.6.2 Calculation of phase II sample size based on stopping for futility

Sample size calculation for phase II of this trial are based on the comparison between the treatment schedules (BI 6727 combined with cytarabine) and the control schedule (cytarabine mono therapy)

The calculation of the phase II sample size is based on a stopping for futility approach (R07-2799, R07-2798). The calculated sample size is based on the assumption that the actual phase II trial represents an interim analysis of a (hypothetical) phase III trial that tests on stopping for futility. The test decision (with respect to phase II) is made by looking at the conditional p-value obtained at the time of interim analysis and comparing it to a given fixed value, the critical p-value. Obviously, in this setting, the critical p-value equals the type I error probability. A characteristic that can be derived from the critical p-value is the conditional power. It provides quantitative information about the probability that a treatment schedule will show superiority compared to a control schedule subject to the response information available at interim analysis.

It is assumed that the response rate of the mono treatment schedule (control schedule) is given as 15%, whereas the response rate of a combination therapy is 30%. The overall type I error is chosen as 5% (one-sided), the overall power as 65%, and the information fraction (number of patients at interim analysis divided by total number of patients) as 60%.

Altogether this leads to a sample size of 86 patients for the interim analysis, i.e. 43 per treatment schedule. With respect to the (hypothetic) interim analysis, which is the actual phase II comparison, a power of 78.3% and a type I error (the critical p-value) of 18.9% is achieved with a critical conditional power value of 23.6% (under the current trend hypothesis, see R07-2799; all calculations performed with EAST 5).

In summary, this means that with a total sample size of 86 patients (43 patients per treatment schedule) a power of 78.3% can be achieved with a type I error of 18.9 % and a critical conditional power of 23.6%.

If the response rate of the combination therapy is assumed to be 25 % instead of 30 % the calculated sample size, leading to the identical power values and error probabilities as above, rises to 174 patients (87 per treatment schedule).

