7.5 SECONDARY ENDPOINTS

Event-free survival (EFS)

EFS will be analyzed with the Kaplan-Meier method for each of the treatment arms as well as overall treatments. An exploratory (non-stratified) logrank test will be used to compare the different treatment arms. For phase II Kaplan-Meier curves for EFS in the genetic subgroups defined in [Section 6.4](#) will be presented separately.

The percentage of patients who are event free will be displayed at monthly or greater time intervals as appropriate.

Patients for whom no leukemia assessment is available within 42 days prior to discontinuation from treatment will be examined on a case by case basis. A listing will be provided.

Overall survival

Overall survival will be analyzed in a manner similar to that of event-free survival.

Remission duration

Remission duration will be summarized by treatment group. Kaplan-Meier plots of the relapse-free survival will be displayed without displaying hazard rates, associated confidence intervals and p-values. Expected duration of response will be calculated based on an exponential model if appropriate.

Note that for remission duration no formal comparison between different treatment arms will be done since remission duration is based on a non-randomised set and therefore possibly biased.

ECOG performance score

The proportion of patients with improved (decreased), and with unchanged, ECOG at end of treatment with respect to baseline will be tabulated.

BI 6727 plasma concentration

See section [7.7.5](#)

Incidence and intensity of adverse events graded according to CTCAE

See section [7.7](#)

Pharmacodynamic monitoring

Analysis of pharmacodynamics will be performed separately and will not be contained in the CTR.

Pharmacogenetics

Analysis of pharmacogenetics will be performed separately and will not be included in the CTR.

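### SAP 5.2.3 leaves out, for relapse-free survival and remission duration, the lost-to-follow-up exclusion that the SAP states for EFS, OS and observation time

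*SAP*

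**What the plan says.** SAP 5.2.3 defines relapse-free survival (RFS) and remission duration for patients whose best overall response is CR or CRi. For those without recurrence or death at the time of analysis, "Relapse-free survival (censored) [in days] = (date of last trial visit (or follow-up) - date of first occurrence of CR or CRi" after trial entry, plus one day. Remission duration inherits the rule: "Remission duration is defined analogously with the exception of censoring patients that die before recurrence".

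SAP 5.2.2 describes the OS censoring date in the same terms and then adds: "Date of last visit does not include visit dates from follow-up where 'lost to follow-up' = yes". The same sentence stands in SAP 5.2.1 for EFS and in SAP 5.3.2 for total observation time. It does not stand in SAP 5.2.3.

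The times are used in SAP 7.5. For RFS, "Kaplan-Meier plots of the relapse-free survival will be displayed without displaying hazard rates, associated confidence intervals and p-values". For remission duration, "Expected duration of response will be calculated based on an exponential model if appropriate". SAP 7.5 also rules out a formal comparison of remission duration between arms, because responders are not a randomised set.

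Protocol 6.2.3.2 sets the contact schedule after end of treatment: "Follow-up visits should be performed at 12 weeks intervals or earlier if appropriate". Telephone contact is allowed.

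**The concern.** A follow-up record flagged as lost documents that the patient was not reached. Its date tells us nothing about whether the patient was alive or in remission. The SAP recognises this for EFS, OS and observation time. If the date is still admitted for RFS and remission duration, one patient can have two different last dates in the same report. Relapse-free time could then run past the date on which the patient was last known to be alive, although death is itself an RFS event.

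What is at stake is the description of how long remissions last. Responders will be few, so one or two such records could visibly move an exponential mean or the tail of a Kaplan-Meier curve, and towards longer remission.

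**Working it through.** The documents give no figure for this point. The check is a comparison of the texts, then a direction argument, then an illustration of size.

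**1. The censoring rules side by side**

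- EFS (SAP 5.2.1, patients without a new anti-leukaemia therapy): last visit including follow-up; exclusion stated.
- OS (SAP 5.2.2): last trial visit or follow-up; exclusion stated.
- Total observation time (SAP 5.3.2): last visit including follow-up; exclusion stated.
- RFS (SAP 5.2.3): last trial visit or follow-up; no exclusion.
- Remission duration (SAP 5.2.3): by analogy with RFS; no exclusion.

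No general rule fills the gap. SAP 6.6, 6.7 and 6.8 do not define a last visit. The note in SAP 6.1.3 that loss to follow-up ends a period concerns the analysing treatment periods. SAP section 4 lists a change to RFS and remission duration (CRi added) but no different censoring date.

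**2. One patient, read literally**

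Take a responder with first CR or CRi on day *c*, last reached on day 200, with a loss entry dated day 284 (200 + 84). These days are assumed.

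- OS and EFS are censored at day 200.
- RFS as written: 284 − *c* + 1 days.
- RFS with the exclusion: 200 − *c* + 1 days.
- Difference: 84 days in which the patient was not known to be alive or relapse-free.

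**3. Direction**

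- *Kaplan-Meier.* Each step multiplies the curve by 1 − d/n, with d events among n at risk. Later censoring leaves every d unchanged and can only keep n the same or increase it, so no factor falls and the curve is never lower.
- *Exponential model.* Mean = T/e, with T the total time at risk and e the events. With k lost responders and a gap of g days it becomes (T + kg)/e. The relative increase is kg/T, which is never negative.

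A simulation of 4,000 runs agreed. It assumed 13 responders, a mean remission of 365 days, about 2.2 lost on average and an 84-day gap. The Kaplan-Meier estimate was never lower at day 180 or day 365 under the later censoring. On average it was 2.5 percentage points higher at day 365, and time at risk was 7.3% greater.

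**4. Illustration of size**

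Inputs from Protocol 7.6.2: 43 patients per arm and assumed response rates of 30% and 15%, hence 43 × 0.30 = 12.9 and 43 × 0.15 = 6.45 responders. Assumptions not in the documents: the number lost (k), the gap (g = 84 days, one 12-week interval) and 150 observed days per responder.

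With 13 responders, T = 13 × 150 = 1,950 days:

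- k = 1: 84/1,950 = 4.3%
- k = 2: 168/1,950 = 8.6%
- k = 3: 252/1,950 = 12.9%

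With 6 responders, T = 6 × 150 = 900 days: 84/900 = 9.3% for k = 1 and 168/900 = 18.7% for k = 2.

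The result depends heavily on T and g. For 13 responders, keeping g = 84 but setting T to mean × events gives:

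- one lost, mean 365 days, 7 events: 84/(365 × 7) = 3.3%
- three lost, mean 180 days, 6 events: 252/(180 × 6) = 23.3%

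With g = 28 the first of these falls to 28/2,555 = 1.1%. With no such patient, or a loss entry dated at the last contact, the effect is zero.

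**The case against.** The strongest reply is that this is a drafting gap. SAP 5.2.2 uses the same phrase for the censoring date and then says what it excludes, so a programmer could carry the exclusion into the next section. That reading is reasonable but not secure: the authors repeated the sentence in three places rather than relying on one definition.

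Two safeguards exist. SAP 5.2.1 requires case-by-case review of patients with neither progression nor death, which would cover most responders censored for RFS. Protocol 7.4 says that response and progression status of patients lost to follow-up will be assessed at the end of the trial. Both reduce the risk. Neither sets the RFS censoring date, and the review is written for EFS.

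The trigger is also narrow. Treatment continues until progression, with frequent visits in each 28-day cycle, and the 12-week interval applies only after end of treatment. The affected patient must be a responder, be lost while still in remission, and have a loss entry dated after the last contact.

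A reader might infer three stronger claims, none of which the documents support:

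- *That reported remission durations are inflated.* The documents do not say how many responders are lost in remission or how a loss entry is dated.
- *That 84 days is the most a lost patient can add.* Protocol 6.2.3.2 allows earlier contacts, and nothing limits when a loss is recorded. The figure is a plausible gap, not a bound.
- *That the whole difference between the two rules is bias.* If loss is unrelated to relapse, censoring at last contact is the sound choice and the later date is too long. If patients are lost only when still in remission at the missed contact, censoring at last contact can be too short. The documents do not establish the mechanism.

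**Conclusion.** The omission is confirmed, and no other part of the SAP supplies the rule. Followed as written, SAP 5.2.3 can censor RFS and remission duration later than the same patient's OS and EFS. Relative to the EFS/OS rule, the effect on the Kaplan-Meier plot and the exponential estimate is one-directional: none, or upward. Confidence is high in the omission and its direction, but not in its size, which cannot be computed from the documents. The 4% to 13% illustration rests entirely on the assumed 13 responders, 150 observed days each, 84-day gap and one to three losses.

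The consequence is limited. The primary endpoint, CR or CRi, is untouched. The endpoints concerned are secondary and exploratory, RFS is plotted without hazard rates, confidence intervals or p-values, and remission duration has no formal comparison between arms. The wording should still be aligned: it contradicts the SAP's own practice and any error favours longer remission.

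**What to change.** Add to SAP 5.2.3, stated to apply to both RFS and remission duration, the sentence already used elsewhere in the SAP: "Date of last visit does not include visit dates from follow-up where 'lost to follow-up' = yes".

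Nothing further is needed. Censoring at the last contact with known disease status would be a different rule. EFS (for patients without a new therapy) and OS take the last visit including follow-up, which may be a telephone contact, so a disease-status rule for RFS alone would create a new inconsistency.

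The cost is one sentence. It uses a follow-up flag that the EFS and OS definitions already require, and no new data. Reported durations would stay the same or become somewhat shorter.
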